7.8.2 Laboratory data

The analyses of laboratory data will be descriptive in nature and will be based on BI standards "Display and Analysis of Laboratory Data" ([9](#)).

Analyses will be based on normalised values, which means transforming to a standard unit and a standard reference range. The original values will be analysed if the transformation into standard unit is not possible for a parameter.

Descriptive statistics of laboratory values over time and for the difference from baseline (see [Section 6.7](#)) will be provided. Frequency tables of changes between baseline and last value on treatment with respect to the reference range will be presented.

Possibly clinically significant abnormal laboratory values are only those identified either in the Investigator's comments or at the Report Planning Meeting at the latest. It is the Investigator's responsibility to decide whether a lab value is clinically significant abnormal or not. Standard or project-specific rules for flagging clinically significant values in an automated manner will not be applied in this study.

Clinically relevant findings in laboratory data will be reported as baseline conditions (prior to first administration of study treatment) or as AEs (after first administration of study treatment) if judged clinically relevant by the investigator, and will be analyzed as such.

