#### 5.2.6.1.4 Adverse events of special interest

The term adverse events of special interest (AESI) relates to any specific AE that has been identified at the project level as being of particular concern for prospective safety monitoring and safety assessment within this trial, e.g. the potential for AEs based on knowledge from other compounds in the same class. AESIs need to be reported to the sponsor’s Pharmacovigilance Department within the same timeframe that applies to SAEs, please see [Section 5.2.6.2.2](#).

The following are considered as AESIs:

- **Hepatic injury**  
A hepatic injury is defined by the following alterations of hepatic laboratory parameters:
  - o An elevation of AST (aspartate transaminase) and/or ALT (alanine transaminase)  $\geq 3$ -fold ULN combined with an elevation of total bilirubin  $\geq 2$ -fold ULN measured in the same blood sample, or
  - o Aminotransferase (ALT, and/or AST) elevations  $\geq 10$  fold ULN

These lab findings constitute a hepatic injury alert and the subjects showing these lab abnormalities need to be followed up according to the ‘DILI checklist’ provided in the ISF. In case of clinical symptoms of hepatic injury (icterus, unexplained encephalopathy, unexplained coagulopathy, right upper quadrant abdominal pain, etc.) without lab results (ALT, AST, total bilirubin) available, the Investigator should make sure that these parameters are analysed, if necessary in an unscheduled blood test. Should the results meet the criteria of hepatic injury alert, the procedures described in the DILI checklist should be followed.

Proprietary confidential information © 2019 Boehringer Ingelheim International GmbH or one or more of its affiliated companies

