#### 5.2.6.2.2 AE reporting to the sponsor and timelines

The Investigator must report SAEs, AESIs, and non-serious AEs which are relevant for the reported SAE or AESI, on the BI SAE form via fax immediately (within 24 hours) to the sponsor's unique entry point (country specific contact details will be provided in the ISF). The same timeline applies if follow-up information becomes available. In specific occasions the Investigator could inform the sponsor upfront via telephone. This does not replace the requirement to complete and fax the BI SAE form.

With receipt of any further information to these events, a follow-up SAE form has to be provided. For follow-up information, the same rules and timeline apply as for initial information.

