Proprietary confidential information © 2019 Boehringer Ingelheim International GmbH or one or more of its affiliated companies

Previous and concomitant therapies will be presented per treatment group without consideration of time intervals and treatment periods.

Laboratory data will be compared to their reference ranges. Values outside the reference range as well as values defined as possibly clinically significant will be highlighted in the listings. Additionally, differences from baseline will be evaluated.

Vital signs or other safety-relevant data will be assessed with regard to possible on-treatment changes from baseline.

Relevant ECG findings will be reported as AEs.

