4. CHANGES IN THE PLANNED ANALYSIS OF THE STUDY

The CTP states in Section 7.3.4 that AEs occurring after the residual effect period but prior to next intake or end of trial termination date will be assigned to “follow-up”. As a more conservative approach, all AEs occurring after intake of trial medication and prior to next intake or end of trial termination date will be assigned to the on-treatment period of the respective trial medication. I.e., no follow-up phases will be defined in this trial, cf.

Table 6.1: 2.

All other analyses described in this TSAP are in accordance with the statistical methods described in the revised CTP.

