7.8.1 Adverse Events

AEs will be coded with the most recent version of MedDRA.

The analyses of AEs will be descriptive in nature. All analyses of AEs will be based on the number of subjects with AEs and not on the number of AEs.

For analysis, multiple AE occurrence data on the eCRF will be collapsed into one event provided that all of the following applies:

- All AE attributes are identical (lower level term, intensity, action taken, therapy required, seriousness, reason for seriousness, relationship, outcome, AESI)
- The occurrences were time-overlapping or time-adjacent (time-adjacency of two occurrences is given if the second occurrence started at most 1 hour after the first occurrence ended)

For further details on summarization of AE data, please refer to "Analysis and Presentation of Adverse Event Data from Clinical Trials" (7) and "Handling of missing and incomplete AE dates" (3).

The analysis of AEs will be based on the concept of treatment emergent AEs. That means that all AEs will be assigned to screening or on-treatment phases as defined in [Section 6.1](#). AEs will be analysed based on actual treatments, as defined in [Table 6.1: 2](#).

An overall summary of AEs will be presented. This overall summary will comprise summary statistics for the class of other significant AEs according to ICH E3 (8) and for the class of AESIs.

CTP: *The following are considered as AESIs:*

- *Hepatic injury*
A hepatic injury is defined by the following alterations of hepatic laboratory parameters:
 - *An elevation of AST (aspartate transaminase) and/or ALT (alanine transaminase) ≥3-fold ULN combined with an elevation of total bilirubin ≥2-fold ULN measured in the same blood sample, or*
 - *Aminotransferase (ALT, and/or AST) elevations ≥10 fold ULN*

The investigator had to classify on the eCRF whether an observed AE was an AESI or not.

According to ICH E3 (8) AEs classified as "other significant" need to be reported and will include those non-serious and non-significant AEs

- (i) which are marked haematological or other lab abnormalities, or
- (ii) which were reported with "action taken = discontinuation" or "action taken = reduced", or
- (iii) which lead to significant concomitant therapy as identified by the Clinical Monitor/Investigator at a Medical Quality Review Meeting.

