The frequency of subjects with AEs will be summarised by treatment, primary SOC and preferred term. AEs which were considered by the investigator to be drug related will be summarised separately. Separate tables will also be provided for subjects with SAEs, subjects with AESIs and subjects with other significant AEs (according to ICH E3 (8)). The frequency of subjects with AEs and the frequency of subjects with AEs considered by the investigator to be drug related will also be summarised by maximum intensity, primary SOC and preferred term.

The SOCs and preferred terms within SOCs will be sorted by descending frequency over all treatment groups.

For disclosure of AE data on ClinicalTrials.gov, the frequency of subjects with non-serious AEs occurring with an incidence of greater than 5 % (in preferred terms) will be summarised by treatment, primary SOC and preferred term. The frequency of subjects with SAEs will also be summarised.

For disclosure of AE data in the EudraCT register, the frequency of AEs, the frequency of non-serious AEs with an incidence of greater than 5 % (in preferred terms) and the frequency of SAEs will be summarized.

For support of lay summaries, the frequency of subjects with drug-related SAEs will be summarized by treatment, primary SOC and preferred term.

If the subject reports headaches during the treatment period further information about the duration of headache, location, characteristics, and signs and symptoms were recorded. The information will be summarized with descriptive statistics.

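### The hepatic-injury AESI is defined by laboratory value, but the SAP counts it only from the investigator's eCRF classification and does not check it against the AST, ALT and bilirubin data

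*SAP*

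**What the plan says.** **Definition.** Protocol 5.2.6.1.4 names one AESI: "A hepatic injury is defined by the following alterations of hepatic laboratory parameters". There are two limbs. The first is AST and/or ALT at least 3-fold ULN together with total bilirubin at least 2-fold ULN in the same blood sample. The second is "Aminotransferase (ALT, and/or AST) elevations ≥10 fold ULN", as SAP 7.8.1 repeats it. Neither limb contains a judgement of clinical relevance.

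**Route into the count.** SAP 7.8.1 states: "The investigator had to classify on the eCRF whether an observed AE was an AESI or not". The AESI output belongs to the adverse event analysis: "Separate tables will also be provided for subjects with SAEs, subjects with AESIs and subjects with other significant AEs".

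**Laboratory analysis.** SAP 7.8.2 limits possibly clinically significant values to those named in the investigator's comments or at the Report Planning Meeting, and adds: "Standard or project-specific rules for flagging clinically significant values in an automated manner will not be applied in this study". It plans descriptive statistics over time, differences from baseline, and a frequency table of changes from baseline to the last on-treatment value relative to the reference range. SAP 7 lists all individual values. Protocol 7.3.4 says: "Values outside the reference range as well as values defined as possibly clinically significant will be highlighted in the listings".

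**The concern.** An event that can be read directly from stored laboratory data is counted only through a manual step, namely an AE record plus an AESI classification. By the general rule in Protocol 5.2.6.1.1, which SAP 7.8.2 echoes, a laboratory change becomes an AE when the investigator judges it clinically relevant. If the site overlooks a sample that meets the limits, the AESI table is one subject short and no planned analysis step sets the two sources against each other.

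At stake is the reliability of a statement that no hepatic-injury AESI occurred on a given formulation and food state. Protocol 1.4.2 says the trial must detect liver laboratory changes in good time, so this is the safety statement a reader is most likely to rely on. No pharmacokinetic endpoint is affected.

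**Working it through.** The plan gives no figure to reproduce. The check has three parts: which samples reach the value-based table, which displays would show an unreported event, and how much one subject weighs.

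**1. Samples that reach the shift table**

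Inputs: the footnotes to Protocol Table 5.2.3: 1 place post-dose safety laboratory samples on Days 2, 7, 11 and 14 of each period, plus the end-of-trial examination. SAP Table 6.1: 2 runs each on-treatment phase to the next dose or to the end of participation. SAP 7.8.2 uses the last on-treatment value.

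| Period | Scheduled post-dose samples | Used as last value | Not used |
|---|---|---|---|
| 1 | 4 | 1 (Day 14) | 3 |
| 2 | 4 | 1 (Day 14) | 3 |
| 3 | 4 + 1 end of trial = 5 | 1 (end of trial) | 4 |
| Total | 13 | 3 | 10 |

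For 24 completers: 24 × 13 = 312 samples, of which 24 × 3 = 72 enter the table and 24 × 10 = 240 do not. In periods 1 and 2 the last scheduled sample is at 312 h. With the half-life range of 54.8 to 82.5 h in Protocol 3.2, that is 312/82.5 = 3.8 to 312/54.8 = 5.7 half-lives after dosing.

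**2. Where a threshold-meeting sample that the site did not report would show**

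| Display | Back in range by the last value | Still raised at the last value |
|---|---|---|
| AESI and other AE tables (SAP 7.8.1) | No | No |
| Shift table (SAP 7.8.2) | No | Yes, but only as above range; 10-fold ULN looks like just above ULN |
| By-time-point statistics, including maximum (SAP 7 and 7.8.2) | Yes, one parameter at a time | Yes, one parameter at a time |
| Individual listings (SAP 7; highlighting in Protocol 7.3.4) | Yes | Yes |

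The first limb needs AST or ALT and bilirubin raised in the same sample. Separate maxima for each parameter cannot establish that; the listings can, but only by inspection. If the site recorded an AE without classifying it as an AESI, the subject would be in the general AE tables but not in the AESI table.

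**3. Weight of one subject**

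Protocol Table 3.1 has 12 sequences for 24 subjects, so 24/12 = 2 per sequence. Treatment A is in 8 sequences (8 × 2 = 16 subjects), and B, C, D and E are in 7 each (7 × 2 = 14 subjects). One missed subject is therefore 1/16 = 6.3% for A, 1/14 = 7.1% for each of the others, and 1/24 = 4.2% overall.

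**The case against.** The strongest reply is that the protocol leaves the site no discretion. Protocol 5.2.6.1.4 treats these findings as an alert that must be followed up, Protocol 5.2.6.2.1 requires all AESIs on the CRF, and Protocol 5.2.6.2.2 says: "The Investigator must report SAEs, AESIs, and non-serious AEs which are relevant for the reported SAE or AESI", within 24 hours. Protocol 3.3.4.1 lists the first limb as a reason for discontinuing treatment, and Protocol 8.3.2 provides for source verification and monitoring. This stands. A reader might infer that the plan allows a threshold-meeting value to go uncounted, or that the SAP replaces a numeric definition with a judgement. The documents do not support either reading: the SAP repeats both limits, and its eCRF sentence says who records the event. A miss would be a site error that the described analysis would not look for. The limits are also fixed multiples of ULN, so open-label conduct leaves little room for bias.

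A second reply is that nothing disappears. This also stands: the listings hold every value, Protocol 7.3.4 highlights those out of range, and a 10-fold elevation would be conspicuous as a maximum among 14 to 16 subjects. None of these displays counts subjects or reconciles the two sources, however.

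A third reply is that the sponsor's laboratory display standard and the ADS Plan, both cited in the SAP, are not available and may contain further displays or checks. That is possible, but SAP 7.8.2 expressly excludes standard flagging rules.

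**Conclusion.** The point holds as a cheap improvement of low priority. The SAP does not derive the hepatic-injury criterion from the laboratory data or reconcile it with the eCRF classification, and its only value-based frequency table leaves out 10 of 13 scheduled post-dose samples per completer. A transient elevation that met the limits and was not reported would enter no frequency table.

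The size is small. Few events are expected: Protocol 1.2.1.5 reports no protocol-specified AESI in the first-in-human trial. The 6.3 to 7.1 percentage points are simply the weight of one subject in any table here, and safety is analysed descriptively without testing. The figures assume planned numbers, full completion, no unscheduled samples, and Day 14 counted as the last on-treatment value of periods 1 and 2.

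Three further inferences are tempting but not supported:

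- **A protocol threshold for possibly clinically significant values.** Protocol 7.3.4 gives no cut-off and promises highlighting, not a count. SAP 7.8.2 fills in who names such values.
- **An undeclared change.** Because SAP 7.8.2 elaborates the protocol here, the statement in SAP 4 that "All other analyses described in this TSAP are in accordance with the statistical methods described in the revised CTP" is not contradicted on this point.
- **A role for the Report Planning Meeting in the AESI count.** SAP 7.8.2 gives that meeting a role only for possibly clinically significant values; for AESIs the SAP names the investigator.

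**What to change.** - **SAP 7.8.1:** derive both limbs of Protocol 5.2.6.1.4 from every on-treatment laboratory sample, with AST/ALT and bilirubin taken from the same sample for the first limb. Count subjects meeting either limb by treatment. List every disagreement between the derived flag and the eCRF AESI classification, with the investigator's assessment alongside.
- **SAP 7.8.2:** exempt this derived hepatic flag from the sentence excluding automated rules, and present the shift table for the worst as well as the last on-treatment value.

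The CRP and ESR limits in Protocol 3.3.4.1 need not be added. They are discontinuation criteria for individual subjects, and nothing in the documents makes them analysis endpoints.

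The cost is a few lines of SAP text, one small derivation, one extra shift display, and an occasional line of comment where the two sources differ. It needs no new samples, thresholds or subjects, and the investigator's assessment is kept.

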7.8.3 Vital signs

The analyses of vital signs (blood pressure and pulse rate) will be descriptive in nature. Descriptive statistics of vital signs over time (baseline and on-treatment measurements, cf. [Table 6.1: 2](#), only) and for the difference from baseline (see Section 6.7) will be provided.

Clinically relevant findings in vital signs data will be reported as baseline conditions (prior to first administration of study treatment) or as AEs (after first administration of study treatment) if judged clinically relevant by the investigator, and will be analyzed as such.

7.8.4 ECG

Relevant ECG findings will be reported as relevant medical history/baseline condition (if a condition already exists before first administration of study treatment) or as AE (if condition emerges after first administration of study treatment) and will be summarized as such. No separate listing or analysis of ECG findings will be prepared.

7.8.5 Others

Physical examination findings will be reported as relevant medical history/baseline condition (if a condition already exists before first administration of study treatment) or as AE (if condition emerges after first administration of study treatment) and will be summarized as such. No separate listing or analysis of physical examination findings will be prepared.

Reports of C-SSRS will be reported as AEs as described in CTP Section 5.2.6.1.7 and will be summarized as such. Results of the C-SSRS will only be listed. No further analysis will be prepared.

Clinically relevant findings of the neurological examination will be reported as relevant medical history/baseline condition (if a condition already exists before first administration of study treatment) or as AE (if condition emerges after first administration of study treatment) and will be summarized as such. No separate listing or analysis of neurological examinations will be prepared.

10. HISTORY TABLE

Table 10: 1 History table

Version	Date (DD-MMM-YY)	Author	Sections changed	Brief description of change
Final	06-AUG-2019		None	This is the final TSAP
